-	Study Week		Week 0	Week 1	Week 2	Week 3	Week 4	Week 5	Week 6 or ET at week 6	Week 7	Week 8	Week 9	Week 10	Week 11	Week 12	Any visit other than at week 6
Medical His	tory	X														
Physical Ex	am	Х														
MINI		Х														
Pregnancy Test (Females only)		X														
Post-Screer Pregnancy Checklist	ning		X			Х			X			Х				
ECG		Х							Х						Х	Х
Labs (CMP, Panel, CBC CRP, IL6, T	, Hs- NFα)	X							X						Х	X (only CMP, Lipid panel, and CBC)
Lab (HbA10	C) ⁴	Х														
Vital Signs		X	Х	Х	Х	Х	Х	Х	Х	Х	Х	Х	Х	Х	Х	Х
Height		X	Х													
Weight		X	Х	Х	Х	Х	Х	Х	Х	Х	Х	Х	Х	Х	Х	Х
Waist Circumferer	nce		Х						Х						Х	
TLFB ¹		Х	Х	Х	Х	Х	Х	Х	Х	Х	Х	Х	Х	Х	Х	Х

VAS	Х	Х	Х	Х	Х	Х	Х	Х	Х	Х	Х	Х	Х	Х	Х
Urine Drug Screen	Х	Х	Х	Х	Х	Х	Х	Х	Х	Х	Х	Х	Х	Х	Х
Fagerstrom Test	Х							Х						Х	
Adverse Events		Х	Х	Х	Х	Х	Х	Х	Х	Х	Х	Х	Х	Х	Х
PANSS		Х						Х						Х	
SANS		Х						Х						Х	
CDRS		Х						Х						Х	
CGI-S and CGI-I ²		Х						Х						Х	
CSSRS	Х	Х						Х						Х	Х
QOL		Х						Х						Х	
EPS Scales (BAS, SAS, AIMS)		Х						Х						Х	
Drug dispensing		Х	Х	Х		Х		Х		Х		Х			
Supportive Counseling		Х	Х	Х	Х	Х	Х	Х	Х	Х	Х	Х	Х	Х	

1- TLFB at screening will be completed for the past 30 days. All other visits the TLFB will collect information for the past week.

2- CGI-I will not be administered at baseline. Only CGI-S is administered at baseline.

- 3- EOT end of treatment
- 4- Lab (HbA1C) will only be performed at the screening visit

5- If ET falls on week 6, the visit should follow regular week 6 protocol. If ET falls on any other visit, follow ET protocol

Informed Consent Process: All subjects will sign IRB approved informed consent form (ICF) prior to starting any study related screening procedures. The written informed consent will be obtained by authorized study personnel. The authorized study staff will explain the study objectives, risks and benefits and overview of the study procedures to all subjects as part of the consent process.

Eligibility Review: An eligibility review will be conducted by the investigator at each site as per the inclusion exclusion criteria listed in section D of the protocol. All subject eligibility criteria will be reviewed by UMass designee prior to subject randomization.

Demographics and Medical/Psychiatric History: Subject's demographics, medical and psychiatric history will be collected as part of the screening process. All patient medical and psychiatric history will be reviewed by the investigator.

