"No desire at all" (marked with a "0") and on the left side with "Worst imaginable desire" (marked with a "100" with a line connecting the two ends. Subjects will mark the appropriate point to indicate where their "desire for substance" falls on this line.

Fagerstrom Test: The Fagerstrom Test for Nicotine Dependence will be used to assess smoking status. Data on subjects will be collected using the Fagerstrom test as per the schedule of events.

Positive and Negative Syndrome Scale (PANSS): PANSS is a measure used to assess symptom severity in patients with schizophrenia. It consists of three sections: Positive scale has 7 items, Negative scale has 7 items and General

Psychopathology has 16 items. Each item (symptom) will be scored on a 7-point scale with higher scores representing increasing levels of psychopathology: 1) Absent, 2) Minimal, 3) Mild, 4) Moderate, 5) Moderate severe, 6) Severe, and 7) Extreme. The PANSS will be administered by a designated study staff at time points specified in the schedule of events.

Schedule of Assessment of Negative Symptoms (SANS): SANS is a 24-item scale used to assess negative symptoms based on observation and a structured interview in patients with schizophrenia. Designated study staff will administer the SANS at baseline, week 6 and week 12.

Calgary Depression Rating Scale (CDRS): The Calgary Depression Rating Scale is used to depression symptoms in subjects. The PI or a designated staff will administer the CDRS at baseline, week 6 and week 12.

Clinical Global Impression – Severity and Clinical Global Impressions – Improvement Scales (CGI-S and CGI-I): The CGI-S and CGI-I are observer rated scales. The CGI-S measures illness severity on a 7-point Likert scale 1) Normal, not at all ill, 2) Borderline mentally ill, 3) Mildly ill, 4) Moderately ill, 5) Markedly ill, 6) Severely ill, and 7) Among the most extremely ill patient. The CGI-I is used to measure improvement in illness and also uses a 7 point Likert scale: 1) Very much improved, 2) Much improved, 3) Minimally improved, 4) No change 5) Minimally worse, 6) Much worse, 7) Very much worse. The PI or a designated study staff will administer this at time points as per the schedule of events.

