Study intervention: Brexpiprazole switch: For the brexpiprazole group, an overlap and taper switch method will be used. The current antipsychotic medication will be tapered following standard clinical practice and discontinued over a time period of 6 weeks. Brexpiprazole will be started at 1mg/day for 4 days, and 2mg/day for 3 days, and then titrate by up to 1mg/day increase every 3 days to reach 4mg/day, or as much and as fast as the participant can tolerate. Participants will stay on 4mg/day or the highest tolerable dose until the end of the study.

Medication adherence will be measured via pill counts at weekly visits. The study staff will discuss pill count data with participants to emphasize the need to take the study medication.

If participants cannot tolerate brexpiprazole after randomization, it will be stopped, though the participant may continue to be followed on another treatment (ideally their pre-study antipsychotic medication) for the remaining weeks of the study. The subject will then continue the rest of the study on their previous antipsychotic medication.

The following assessments will be completed at baseline visit:

- 1) Anthropometric measures (weight, waist circumference and height at screening to be used) and Vital signs
- 2) Weekly TLFB
- 3) Drug screen
- 4) Post-Screening Pregnancy Checklist
- 5) AE review
- 6) PANSS, SANS, QLS, CGI-S
- 7) C-SSRS, EPS scales, CDRS
- 8) Supportive counseling

Week 6 and week 12 visits: The following assessments will be done at week 6 and 12.

- 1) Anthropometric measures (weight, waist circumference) and Vital signs
- 2) Weekly TLFB
- 3) Drug screen
- 4) Post-Screening Pregnancy Checklist (Week 6 only)
- 5) AE review
- 6) PANSS, SANS, QLS, CGI-S
- 7) C-SSRS, EPS scales, CDRS
- 8) Supportive counseling
- 9) ECG
- 10)Labs (CMP, CBC, lipid panel)
- 11)Labs hs-CRP, IL-6 and TNF-alpha collected and stored at -80F
- 12)Fagerstrom test

Week 2, 3,4,5,7,8,9,10,11 visits: These visits may be completed virtually through a secured platform depending on the most current COVID situation. During the virtual routine follow up visits, vital signs and urine drug screen will be unable to be collected; but all subjects who go through the switch will have demonstrated no clinically significant changes in vitals, ECG, or lab results in prior long visits. The following assessments will be administered at these weekly visits:

- 1) Vital signs and anthropometric measures (weight)
- 2) Urine drug screen

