- 3) Post-Screening Pregnancy Checklist (Week 3 and 9 only)
- 4) TLFB
- 5) AE review
- 6) Supportive counseling

End of Study / Discontinuation of Study Medication – When a participant who is randomized to brexpiprazole completes Visit 12 (or sooner for those discontinuing study medication), he or she will no longer receive medications through the study. There will need to be a discussion with the participant and his/her treatment provider as to whether or not the participant will continue on the study medication after the subject's study participation is over. For participants finishing the study at Visit 12, this discussion should occur about three weeks prior to the final visit. If the participant will continue on the study medication study medications following standard clinical practice. The monitoring and management of symptoms, therapeutic response and medication side effects will be the responsibility of the treatment provider.

Subjects who do not wish to continue on the study medication after the end of study, the treatment provider can begin to manage a cross titration off the study medication and on to either the antipsychotic medication prior to the study or a new antipsychotic medication following standard clinical practice. The monitoring and management of symptoms, therapeutic response and medication side effects will be the responsibility of the treatment provider.

Withdrawal of Subjects

Subjects are free to discontinue their participation in the study at any time and without prejudice to further treatment. The investigator must withdraw any subject from the study who requests to be withdrawn or fits the criteria below:

- 1) If subject meet any exclusion criteria after enrollment.
- 2) If subjects have laboratory results that meet the exclusionary criteria range during the study, the subject will have his/her labs repeated before being withdrawn from the study.
- 3) Subjects will be withdrawn from the study is there is an increase in their PANSS total score greater than or equal to 20 compared to their baseline total score at any point during the study.
- 4) Female subjects may be terminated from the study if they become pregnant at any time while participating in the study.
- 5) If at any time the study sponsor or research personnel at UMass decide to terminate the study, subjects' consent will be withdrawn involuntarily.

Early Termination Visit

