If the subject is terminated from the study on what would be their week 6 visit, they will complete all the assessments that are required in a regular week 6 visit. If the subject is terminated from the study at any other point, only safety procedures will be performed (listed below).

- 1. Vital signs and anthropometric measures (weight)
- 2. Urine drug screen
- 3. TLFB
- 4. AE review
- 5. Safety labs (CMP, CBC, lipid panel)
- 6. ECG
- 7. CSSRS

G. TREATMENT OF SUBJECTS

Study Drug Dose and Administration

The study drug brexpiprazole (Rexulti) will be administered orally. Subjects will be randomly assigned to either switch to brexpiprazole or remain on the same antipsychotic medication (treatment as usual). Subjects randomized to brexiprazole treatment will be titrated as per section F (study intervention). Study participants randomized to brexpiprazole treatment will be titrated to 4mg/day or the highest tolerable dose as per the study MD's clinical judgement until the end of the study. Dose de-escalation due to tolerability will be allowed in the study. If subjects recover, the dose can be increased to the 4mg or the highest tolerable dose as per the MD's clinical judgement. Patients who are unable to tolerate a minimum dose of 1 mg will be withdrawn from the study

Study Drug

Commercially available brexpiprazole will be provided directly to all sites by Otsuka Pharmaceuticals. Study drug will be provided as 1mg and 2mg tablets. Subjects will take medications as dispensed by their site's Investigational drug pharmacy.

Storage and Drug Accountability

The study drug will be stored as per the drug insert. The sites are required to maintain current drug dispensation and accountability logs throughout the study. All unused supplies will be checked against the drug movement records during the study and/or at the end of the study.

Prohibited Medications

Currently on the following antipsychotics

- Aripiprazole
- Cariprazine

Currently on medications to treat substance use such as:

- Disulfiram,
- Naltrexone,
- Acamprosate,
- Methadone,
- Buprenorphine,
- Varenicline
- Bupropion

Special Consideration for Concomitant Medications with Brexpiprazole

Medications	Intervention
-------------	--------------

Strong CYP3A4 inhibitors	With concomitant use of brexpiprazole with a
	strong CYP3A4 inhibitor, reduce the brexpiprazole
Examples: itraconazole,	dosage and administration [see drug insert
clarithromycin, ketoconazole	dosage and administration (2.5)]

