The study will be conducted as per the protocol and will adhere to the GCP standards. The investigators and all study staff should be trained in GCP guidelines.

Informed Consent

The PI must ensure to clearly explain and provide oral and written information on the study purpose, procedures, risks and benefits of participating (including potential risks involving the study medications) to each subject and/or legal guardian. All information should be provided in language that is easy to understand. All subjects must be informed that their participation is voluntary and they can withdraw from the study at any time if they choose. If the subject chooses to participate, he/she or legal guardian must sign the informed consent form and when required, the caregiver must sign the caregiver ICF. Any questions, concerns, or ambiguities will be clarified by the site's PI or another study clinician prior to the patient signing consent.

L. STATISTICS AND DATA ANALYSIS

Intent-to-treat analysis and a mixed model approach will be conducted to estimate the pragmatic effects of brexpiprazole treatment on the number of days of substance use in the past week, substance craving, psychiatric symptoms and quality of life. The entire 12 week duration of treatment, including the 6-week switchover phase, will be included in the analysis. Polynomial time trends (e.g., slopes) will be used to fit the population mean response curve for the control group. Group-by-time interactions will be modeled as a function of time to fit between-group effects. Subject-specific parameters will be estimated to model individual subject deviations from the group mean. Baseline measures of substance use and clinical symptoms will also be included in the model as covariates.

REFERENCES

3. van Dijk D, Koeter MW, Hijman R, Kahn RS, van den Brink W. Effect of cannabis use on the course of schizophrenia in male patients: a prospective cohort study. Schizophr Res. 2012; 137(1-3): 50-7.

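### A PANSS rise of 20 or more ends study participation, not only treatment, so a week 6 trigger stops both primary outcomes for weeks 7-12

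*Combined protocol and SAP*

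**What the plan says.** Section F (Withdrawal of Subjects) obliges the investigator to withdraw from the study anyone who meets a listed criterion. Criterion 3 reads: "Subjects will be withdrawn from the study is there is an increase in their PANSS total score greater than or equal to 20" relative to baseline, at any point. It makes no distinction between arms.

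Section E says of the rating itself: "The PANSS will be administered by a designated study staff at time points specified in the schedule of events". Table 1 marks PANSS at weeks 0, 6 and 12 only. TLFB and VAS are marked at every visit. For early termination, note 5 to Table 1 says "If ET falls on week 6, the visit should follow regular week 6 protocol". Section F describes no visit after termination.

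The protocol treats intolerance of the drug in two ways. Section F (Study intervention) says that brexpiprazole is stopped but "the participant may continue to be followed on another treatment (ideally their pre-study antipsychotic medication) for the remaining weeks of the study". Section G (Study Drug Dose and Administration) says "Patients who are unable to tolerate a minimum dose of 1 mg will be withdrawn from the study".

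On the analysis, Section L commits to intent-to-treat and adds "The entire 12 week duration of treatment, including the 6-week switchover phase, will be included in the analysis". The only covariates named are baseline ones: "Baseline measures of substance use and clinical symptoms will also be included in the model as covariates".

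**The concern.** An intent-to-treat estimate over 12 weeks needs outcome data after treatment stops. Criterion 3 ends that data collection because the subject has worsened clinically, at the visit where the 6-week taper of the previous antipsychotic is due to finish. A subject triggered then contributes no record from the period fully on brexpiprazole.

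The reason for the loss may be related to outcome. If worsening psychosis goes with rising substance use, and if more brexpiprazole than control subjects trigger, the records lost are mostly unfavourable ones from the brexpiprazole arm. The TLFB and VAS models use each subject's own earlier values. As described, they do not use the week 6 PANSS that caused the missing data.

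At stake is an avoidable loss of primary-outcome data in a 50-subject trial, together with an inconsistent rule on follow-up after the drug is stopped.

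**Working it through.** **The plan's own figure.** Section D: 40 completers at 20% discontinuation need 40 / (1 - 0.20) = 50 randomised. This reproduces. No alpha, power, effect size or SD is given, so there is no power calculation to check.

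**Loss per subject.** Weekly TLFB and VAS give 12 post-baseline records (weeks 1-12). A week 6 termination still has its week 6 record, so the loss is 12 - 6 = 6 of 12 on each outcome (50%). The written lists for weekly and early termination visits omit VAS, but Table 1 marks it at both, so VAS is due in weeks 7-12. An unscheduled PANSS at another time would change the count; none is planned.

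**Does any provision rescue the data?** Continued follow-up in Section F covers brexpiprazole intolerance only. The contact after participation mentioned in Section H is for an occasional missing item or an added question.

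**Loss for the trial.** Scheduled records per outcome: 50 x 12 = 600, of which 50 x 6 = 300 fall in weeks 7-12. The trigger rate is not given; 0 to 6 of 50 is assumed, which stays within the 50 x 0.20 = 10 discontinuations anticipated for all causes.
- 0 triggers: 0 records lost.
- 1 trigger: 6 lost = 1% of 600, 2% of 300.
- 6 triggers: 36 lost = 6% of 600, 12% of 300.

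**Bias at week 12 (all inputs assumed).** No treatment effect. Random intercept and slope model with variances of intercept 0.50, slope 0.25 at week 12 and error 0.25, so the total is 1 SD at week 12. Generalised least squares with known variances, 200,000 simulated subjects per arm, mean of 4 runs. PANSS change is correlated with the TLFB slope.

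| Trigger rate, brexpiprazole vs control | Correlation 0.2 | 0.4 | 0.6 |
|---|---|---|---|
| 20% vs 4%, no later records | 0.015 SD | 0.030 SD | 0.043 SD |
| 20% vs 4%, 3 of 6 later records kept | 0.005 SD | 0.012 SD | 0.020 SD |
| 10% vs 4%, no later records | 0.007 SD | 0.012 SD | 0.018 SD |

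With equal rates, zero correlation or all 6 later records kept, the shift is about 0.

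**Against precision.** With 25 per arm (1:1 assumed), the standard error of the week 12 difference is 0.257 SD with full data. With 5 against 1 triggered (20% vs 4%), it is 0.261 SD with no later records and 0.259 SD with 3 of 6 kept. Largest ratio: 0.043 / 0.261 = 0.16, about one sixth. Another working model would give a somewhat different ratio.

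**What an amendment can still recover.** The synopsis plans enrolment from February 15, 2018 to November 20, 2023 (2,104 days), and this version is dated January 7, 2022 (day 1,422). The share left is (2,104 - 1,422) / 2,104 = 682 / 2,104 = 32%. If accrual was steady (assumed), that is 50 x 0.324 = about 16 subjects. Recoverable records: 0 to 36 x 0.324 = 0 to about 12 of 600 (0%-2%) if every later visit is kept, and half that if half are kept.

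**The case against.** The strongest case is that the effect is small and the rule defensible. Criterion 3 is a plausible protective rule in a 50-subject feasibility study. Subjects enter on a stable antipsychotic dose and are excluded if psychiatrically unstable, so there may be no triggers at all. The largest modelled bias needs 20% against 4% triggering and a correlation of 0.6. Complete data would improve the standard error only from 0.261 to 0.257 SD. All of this stands, and it limits the point to a cheap improvement.

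Three practical objections also stand and shape the fix. A worsened subject may be changed to aripiprazole or cariprazine, or started on a substance-use medication, and criterion 1 would then remove that subject anyway. Recovered brexpiprazole-arm records would be off drug, and the simulation, which assumes no treatment effect, does not show what they do to a real effect. On the weekly visits from week 2, apart from weeks 6 and 12, the protocol says "These visits may be completed virtually through a secured platform depending on the most current COVID situation", but VAS is a line that the subject marks and no remote method is described.

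A reader might go further in three ways, and the documents support none of them:
- That worsening goes unwatched before week 6. Adverse events are reviewed at every visit, worsening of existing conditions is recorded as an adverse event, criterion 1 applies throughout and a medical monitor reviews events.
- That the arms will lose data unequally. Only the brexpiprazole arm changes antipsychotic, so this is plausible, but no rate is given for either arm.
- That every model leaves out the week 6 PANSS. The PANSS model contains it as an outcome; the gap concerns TLFB and VAS.

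**Conclusion.** The point holds as a design weakness of modest size. On the text, a week 6 trigger costs a subject half of the post-baseline records on both primary outcomes, and this conflicts with the analysis window in Section L. That part needs no assumption.

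The size for the trial does rest on assumptions: the number of triggers, their split between arms, the correlation with substance use, 1:1 allocation and the variance components. A reader might infer that the primary result would be materially biased or the trial invalid; the calculation gives no support for that. Nor would an amendment restore everything lost, because about two thirds of the planned enrolment period had passed by this version.

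The case for changing the rule is that the loss is preventable and may be related to outcome, and that the protocol already accepts follow-up after the drug is stopped for intolerance. The conflict between Sections F and G on intolerance should be corrected whatever the PANSS trigger rate.

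**What to change.** 1. Amend criterion 3 so that a PANSS rise of 20 or more stops brexpiprazole, or leads to clinical management in the control arm, without ending participation. Continue TLFB and VAS to week 12 at the visits already scheduled, for subjects who still consent.
2. State that criterion 1 does not end follow-up for these subjects, whether it is met through exclusion 1 (psychiatric instability), exclusion 6 (change to aripiprazole or cariprazine) or exclusion 7 (start of a listed substance-use medication).
3. State in Section L that records after a treatment change stay in the intent-to-treat analysis under the randomised arm.
4. Change the 1 mg sentence in Section G to match Section F, so that intolerance stops the drug and not follow-up.

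**Cost.** Low: one amendment with IRB approval and any matching consent wording. No new assessment is added.

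**Downsides.** There is visit burden for subjects who have worsened. Recovery will be incomplete, because some will miss visits or withdraw consent. Off-treatment records may dilute a drug effect, although this fits the stated pragmatic intent-to-treat aim. VAS must be completed in person or adapted where visits are virtual. The trial would contain two follow-up rules, before and after the amendment.

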Brexpiprazole is a newly approved dopamine D₂ receptor partial agonist for schizophrenia treatment. It shows partial agonism with lower intrinsic activity at

the D₂ receptor and stronger antagonism at the 5-HT_{2A} receptor than aripiprazole (10). We hypothesize that brexpiprazole, similar as aripiprazole, can decrease the level of craving and reduce the use of substance in patients with schizophrenia; further, brexpiprazole may be even more efficacious than aripiprazole in reducing substance use given its relatively lower potential to induce D₂ partial agonist-mediated activating adverse effects such as restlessness, insomnia, and nausea (11), which are common substance withdrawal symptoms.

B. RATIONALE AND STUDY DESIGN

The proposed study is a 4-site, 12-week, novel, feasibility, "proof of concept" investigation of patients who have co-occurring diagnoses of schizophrenia and current substance use disorder (alcohol, cocaine, heroin, or cannabis). Fifty patients not treated with aripiprazole or cariprazine (the other two dopamine receptor partial agonists) at the time of consent will be randomly assigned to switch to brexpiprazole (the brexpiprazole group) or remain on the same antipsychotic treatment (the control group).

C. STUDY OBJECTIVES

The primary objectives of the study include:

1) examine the effect of brexpiprazole treatment on the number of days of substance use in the past week as measured by the Timeline Follow-Back (TLFB) assessment;

2) examine the effect of brexpiprazole treatment on substance craving using 100mm visual analogue scale (VAS).

The secondary objectives are to examine the effect of brexpiprazole treatment on:

1) the dollar amount spent on substances in the past week;

2) the psychiatric symptoms as measured by various clinical rating scales;3) quality of life.

Additional objectives of this study include collection of additional safety data on brexpiprazole using safety parameters (ECG, metabolic labs, vital signs, suicidality, EPS, side effects measured by the SAFTEE) throughout the study

D. STUDY POPULATION

The study will be conducted at 4 sites in the US. We expect to enroll 50 subjects across 4 sites. We anticipate a 20% discontinuation for this study. Hence we will randomize 50 subjects so we will have 40 subjects completing the study.

Eligibility Criteria

Inclusion criteria:

Each subject must meet all study inclusion criteria prior to randomization.

- 1) Age 18-65 years old

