Heinrichs Carpenter Quality of Life Scale (QOL): The QOL is a 21-item scale providing information on symptoms and functioning in patients with schizophrenia. A trained designated study staff will administer the QLS at baseline, week 6 and week 12.

Safety Assessments

Extra Pyramidal Symptoms (EPS) Scales: The PI or a designee will complete the following EPS scales – The Abnormal Movement Scale (AIMS), Barnes Akathasia Scale (BAS) and the Simpson Angus Scale (SAS). These movement scales will be assessed at baseline, week 6 and week 12.

Columbia Suicide Severity Rating Scale (CSSRS): The PI or a designee will administer the C-SSRS. The C-SSRS will be administered at screening,

baseline, week 6 and week 12. The C-SSRS should be administered by a clinician trained to assess and manage suicidal ideation and behavior.

Adverse Events (AE): Adverse events will be monitored at each weekly visit. The PI or the sub-investigator will review adverse events at every study visit. AE information is collected and recorded starting on the day the consent is signed until the end of an individual's participation in the study.

F. STUDY VISIT PROCEDURES AND SCHEDULE

The proposed study is a 4-site, 12-week, novel, feasibility, "proof of concept" investigation of patients who have co-occurring diagnoses of schizophrenia and current substance use disorder (alcohol, cocaine, heroin, or cannabis). Fifty patients not treated with aripiprazole or cariprazine at the time of consent will be randomly assigned to switch to brexpiprazole (the brexpiprazole group) or remain on the same antipsychotic treatment (the control group).

Informed consent will be obtained prior to the screening visit and any study procedures.

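### The EPS scales are classed as safety assessments but left out of the safety-only early-termination visit, so anyone who leaves before week 6 has no post-baseline EPS score

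*Combined protocol and SAP*

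**What the plan says.** - **Objective.** Section C lists as an additional objective the collection of "safety parameters (ECG, metabolic labs, vital signs, suicidality, EPS, side effects measured by the SAFTEE) throughout the study".
- **Schedule.** Section E, under Safety Assessments, names AIMS, BAS and SAS and says: "These movement scales will be assessed at baseline, week 6 and week 12". In Table 1 the row "EPS Scales (BAS, SAS, AIMS") carries three marks, at those same visits, and none in the early-termination (ET) column.
- **Early termination away from week 6.** Section F says: "If the subject is terminated from the study at any other point, only safety procedures will be performed (listed below"). The seven items are vital signs with weight, urine drug screen, TLFB, AE review, safety labs, ECG and C-SSRS.
- **Early termination at week 6.** For these patients Section F says that "they will complete all the assessments that are required in a regular week 6 visit", which includes the EPS scales.
- **Adverse events.** Section E says: "Adverse events will be monitored at each weekly visit".
- **Intolerance.** Section F says: "If participants cannot tolerate brexpiprazole after randomization, it will be stopped". The patient may then stay in follow-up on another treatment.
- **Analysis.** Section L specifies no EPS summary and no rule for missing EPS ratings.

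**The concern.** The protocol classes these scales as safety assessments and then leaves them out of a visit that it restricts to safety procedures, without giving a reason. Of the parameters named in the Section C objective, ECG, metabolic labs, vital signs and suicidality are all measured at the ET visit. The EPS scales are not.

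The omission matters because of when the first post-baseline rating falls. Starting brexpiprazole, titrating it and tapering the previous antipsychotic all take place before or up to week 6. A patient who leaves in that window contributes a baseline score and nothing after it. If the reason for leaving is akathisia or another EPS, the missing score depends on the outcome being measured. Only one arm is starting a new drug, so the loss need not balance between arms. The scale-based EPS result would then lean towards patients who tolerated the switch.

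**Working it through.** **1. The plan's own figure.** Section D gives 50 randomized, 20% discontinuation and 40 completers. Check: 40 / (1 − 0.20) = 50. Expected leavers: 0.20 × 50 = 10, over both arms and for any reason.

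**2. Titration against the rating schedule.** At the fastest pace stated in Section F, counting the first dose as day 1, the steps are 1 mg on days 1–4, 2 mg on days 5–7, 3 mg on days 8–10 and 4 mg from day 11. The first post-baseline EPS rating is at week 6, day 42. Gap: 42 − 11 = 31 days. The previous antipsychotic is tapered over the same 6 weeks.

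**3. EPS data by time of exit.**

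| Exit | Week 6 score | Score at exit | AE review at exit |
|---|---|---|---|
| Before week 6 | No | No | Yes |
| At the week 6 visit | Yes | Yes | Yes |
| Weeks 7–11 | Yes | No | Yes |

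**4. How many leavers fall in each row.** Exit timing is not stated, so three patterns over weeks k = 1 to 11 are assumed, with weight w(k) equal to 1 (uniform), 1/k (early) or k (late). Leavers before week 6 = 10 × [w(1)+…+w(5)] / [w(1)+…+w(11)]. The other columns follow in the same way.

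| Assumed pattern | Before week 6 | At week 6 | Weeks 7–11 | No rating at exit |
|---|---|---|---|---|
| Uniform | 10 × 5/11 = 4.5 | 0.9 | 4.5 | 9.1 |
| Early | 10 × 2.283/3.020 = 7.6 | 0.6 | 1.9 | 9.4 |
| Late | 10 × 15/66 = 2.3 | 0.9 | 6.8 | 9.1 |

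About 9 of 10 leavers have no EPS rating at exit under every pattern. The number with no post-baseline score at all runs from 2.3 to 7.6.

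**5. Brexpiprazole arm alone.** The allocation ratio is not stated. Assuming 25 per arm and equal discontinuation, halve the second column: about 1.1 (late), 2.3 (uniform) or 3.8 (early) patients, for any reason, with no post-baseline score.

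**6. What cannot be computed.** A bias in percentage points would need an EPS rate, the share of exits due to EPS and a threshold for a positive scale. The documents give none of these.

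**The case against.** The strongest reply is that the event itself is not lost. AE review is on the ET list and takes place weekly. Section H has AEs graded for intensity and relatedness and followed until resolved, judged stable or lost to follow-up. A reader might infer that patients who leave with akathisia vanish from the EPS evidence altogether. The documents do not support that. What is missing is the scale score, and a three-level intensity grade cannot be compared with a baseline BAS, SAS or AIMS score. The side-effect instrument named in Section C (SAFTEE) does not appear in Table 1 or the Section F visit lists, so it does not visibly fill the gap.

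Other points on that side also stand:

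- Leavers at week 6 are fully rated, and later leavers keep a week 6 score.
- Dose reduction for tolerability is allowed, and a patient who stops the drug may remain in follow-up, so not every intolerant patient leaves. A patient who stops and stays may, however, be rated at week 6 on the previous antipsychotic. Section G also withdraws patients who cannot tolerate 1 mg. That must be reconciled with the Section F provision, because it decides who reaches an ET visit.
- EPS is an additional objective in a 50-patient proof-of-concept trial, with no planned between-arm test. The Section C wording on collection throughout the study also covers ECG and labs, which are measured only at screening, week 6, week 12 and ET. It does not promise frequent rating.

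A reader might also infer that the gap undermines the rationale in Section A that brexpiprazole is less activating. It does not. That comparison is with aripiprazole, and patients on aripiprazole are excluded, so this trial could not test it however complete the EPS data were.

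**Conclusion.** The omission is real. The Section F list and Table 1 agree on it, so it is not a fault of a broken table. Patients who leave before week 6 have no post-baseline EPS scale score, and those who leave in weeks 7 to 11 have none at exit. For both groups only the AE record describes their state when they left.

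If exits are related to akathisia or EPS, the scale-based result may look too favourable for brexpiprazole. This is a possibility, not a demonstrated bias. Its size is unknown, because it depends on when and why patients leave. The protocol's 20% implies about 10 leavers. Under the assumed exit patterns about 9 of them have no exit rating, and roughly 2 to 8 have no post-baseline score. It is tempting to turn this into an understated akathisia percentage, but any such figure would rest wholly on assumed rates, and the plan has no EPS incidence endpoint to which it would apply.

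The point is limited in scope but worth correcting, because the missing ratings may depend on the outcome and a visit at which to take them already exists.

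**What to change.** 1. Add BAS, SAS and AIMS to the early-termination list in Section F and to the ET column of Table 1, for both arms.
2. State in Section L how EPS will be summarized: the ET rating enters as the last on-study value, the number of patients without a post-baseline rating is given by arm, and the result is shown beside the EPS and akathisia AEs.
3. If a rating is also taken when brexpiprazole is stopped in a patient who stays in the study, list it descriptively and keep it out of the between-arm comparison. Controls have no matching visit, so including it, above all in a worst-score summary, would give one arm extra ratings triggered by symptoms.

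**Cost.** Three scales that the sites already use, at about 10 visits by the protocol's own figure, or at most 10 × 3 = 30 extra ratings. The ET visit already calls for an ECG and a blood draw, so the patient should normally be present. The visit becomes slightly longer.

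**What it will not recover.** Patients who withdraw consent give no further data (Section H), and those who do not attend in person cannot be rated. The interval between baseline and week 6 also stays unrated for patients who remain in the study.
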